v. EEG-based connectivity analysis offers superior temporal specificity for the study of IEDs. Assessment of IEDs using fMRI is limited by the poor temporal specificity of fMRI. IEDs last hundreds of milliseconds whereas blood flow changes measured by fMRI require multiple seconds. In contrast, EEG is a temporally-precise method for studying the impact of IEDs on network connectivity.[37] High-density EEG (HD-EEG) specifically estimates the underlying source of this activity. Surprisingly, however, few EEG connectivity analyses have been done in children with BECTS.[38–41] Only one study assess the impact of IEDs in wakefulness and it is limited by a small sample size of children with only right hemispheric IEDs, thus obscuring the impact of IEDs on language network connectivity. Furthermore, all EEG connectivity studies in BECTS have been done in the resting state, whereas language network connectivity is likely to be better measured when the network is engaged in a task. Therefore, a significant gap persists in understanding connectivity in BECTS.

EEG connectivity analysis has been limited by the concern for volume conduction, a problem that arises when activity in nearby electrodes is correlated not because the regions are connected but rather because the electrodes are picking up neuronal activity from a single common source. Fortunately, new connectivity metrics, such as the **weighted Phase Lag Index (wPLI)**,[42] are quite robust against volume conduction. To calculate wPLI, the EEG signal is broken down into frequency bands (i.e. alpha, beta) and the phase of the waveforms in each band is compared across brain regions; non-zero phase lags are considered true connectivity.[42] wPLI is a continuous metric ranging from 0-1, where 0 indicates no connectivity and 1 indicates perfect connectivity. wPLI offers better spatial-specificity when it is calculated from a high number of EEG electrodes.

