Impact of Repetitive Transcranial Magnetic Stimulation (TMS) on Spike Frequency and Brain Connectivity in Children with Benign Epilepsy with Centrotemporal Spike (BECTS)

Statistical Analysis Plan

NCT04325282

July 9, 2025

We used the Wilcoxon signed-rank test, a non-parametric test appropriate for data that is not normally distributed, to assess changes in IED frequency and brain connectivity (as measured by the weighted Phase Lag Index [wPLI] between six regions of interest, yielding 15 unique region-to-region pairs). First, we measured change *within* each session by comparing post-rTMS to pre rTMS recordings (post vs. pre active rTMS IED & connectivity values; post vs. pre sham rTMS IED & connectivity values). Second, we compared the changes induced by active vs. sham rTMS to one another.

Given the multiple ROIs investigated, we adjusted significance thresholds using principal component analysis, which accounts for the effective number of independent tests. This method is suitable when data in each comparison are not completely independent, as is the case with EEG where signal represents summated activity from multiple regions. In contrast, correction methods that assume complete independence (e.g., Bonferroni) may set overly conservative thresholds that obscure meaningful findings.

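### The SAP drops Bonferroni for a wrong reason, and the PCA test count that replaces it does not guarantee family-wise error control over the 15 wPLI pairs

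*SAP*

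**What the plan says.** The SAP's first paragraph describes wPLI measured "between six regions of interest, yielding 15 unique region-to-region pairs". Each pair is tested with the signed-rank test: within the active session, within the sham session, and then active change against sham change.

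Its second paragraph gives the multiplicity method: "we adjusted significance thresholds using principal component analysis, which accounts for the effective number of independent tests". The reason offered is: "This method is suitable when data in each comparison are not completely independent, as is the case with EEG". Bonferroni is named as an example of the alternative: "In contrast, correction methods that assume complete independence (e.g., Bonferroni) may set overly conservative thresholds that obscure meaningful findings".

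The SAP does not state alpha, the error rate to be controlled, the matrix put into the PCA, the rule for retaining components, the resulting count or threshold, or which of the tests form the family. The protocol contains no multiplicity rule. Its objectives table names one connectivity pair, stimulated motor cortex to left inferior frontal gyrus, and calls for separate calculations on spTMS-EEG and resting-state EEG.

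**The concern.** The argument against Bonferroni starts from a wrong premise. Bonferroni adds up the individual error probabilities, and that sum bounds the family-wise error whatever the correlation between tests. The SAP is right that it can be conservative when tests are positively correlated, but conservative is not invalid. The premise is the stated reason for moving from a method with a guarantee to one without.

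The dependence invoked also describes something other than what is tested. The SAP points to EEG signal, "as is the case with EEG where signal represents summated activity from multiple regions". The tests are on pairwise wPLI changes. The protocol (Literature Review, item v) says that metrics such as wPLI "are quite robust against volume conduction", which is one form of the signal mixing described. Pairs that share a region may still move together, but that correlation has to be taken from the tested changes and cannot be inferred from raw EEG.

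At stake is whether a pair called significant can be relied on. If the effective count is too low, chance findings among the 15 pairs arise more often than the adjusted threshold suggests.

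**Working it through.** **Inputs.** Six regions and 15 pairs (SAP). Paired signed-rank test (SAP). Planned enrolment of 36-40 (protocol, Recruitment & Retention); simulations used n = 38, with n = 20 as a sensitivity case. Assumed, because neither document gives them: a two-sided 5% family-wise level, and the correlation among the 15 changes.

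**Plan's own figure.** 6 x 5 / 2 = 15 pairs, which agrees with the SAP.

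**Bonferroni.** The threshold is 0.05/15 = 0.00333. The bound is 15 x 0.00333 = 5.0% under any dependence. If the tests are independent, the error is 1 - (1 - 0.05/15)^15 = 4.89%. Simulated error ran from 5.0% (independent) down to 1.6% (exchangeable correlation 0.9).

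**PCA count M.** The threshold is 0.05/M, and the bound over 15 tests is 15 x 0.05/M, which exceeds 5% for every M below 15. For example:

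- M = 10: bound 7.5%; 7.2% if independent.
- M = 6: bound 12.5%; 1 - (1 - 0.05/6)^15 = 11.8% if independent. Six is the most components that a PCA of six regional signals could return.

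These are ceilings and independence values. The true rate depends on the correlation, hence the simulation.

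**Simulation.** There were 6,000 null data sets per setting, with multivariate normal differences and exact two-sided signed-rank tests. M was computed from the sample correlation matrix of the 15 differences. Nine structures were used: independent; exchangeable 0.3, 0.5, 0.7 and 0.9; shared-region 0.25 and 0.45; three blocks of five at 0.5 and 0.8. The Monte Carlo standard error is about 0.3 points at 5%.

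| Rule for M | Family-wise error, range over structures and both n |
|---|---|
| Eigenvalue > 1 | 9.8-25.8% |
| 80% of variance | 7.6-15.2% |
| 90% of variance | 5.2-12.0% |
| 95% of variance | 4.0-9.3% |
| Galwey | 4.4-7.2% |
| Li-Ji | 5.2-6.9% |
| Nyholt | 4.0-5.5% |
| 99% of variance | 2.1-5.8% |
| 99.5% of variance | 1.9-5.2% |
| Bonferroni, for comparison | 1.6-5.0% |

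**Proposed replacement.** A separate null simulation generated wPLI from six signals, with and without mixing (38 children, four recordings, 150 epochs, 1,500 trials per setting, standard error about 0.5-1 point). The sign-flip maximum statistic gave 4.3-5.3% and Bonferroni 3.1-4.5%. The mean correlation among the changes there was only 0.06-0.11, a feature of that model and not of the trial.

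**Family size.** Three comparisons on each of 15 pairs make 45 tests. At 0.05/15 each, the bound is 45 x 0.05/15 = 15%, and 1 - (1 - 0.05/15)^45 is about 14% under independence. The three comparisons on a pair are related by construction, so this only illustrates why the family must be stated.

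**The case against.** The strongest defence is that the SAP's practical point is sound. EEG connectivity measures are correlated, each region appears in five of the 15 pairs, and at high correlation Bonferroni wastes error (1.6% at correlation 0.9). Under strict rules an effective-test count comes close to 5%: Nyholt, 99% and 99.5% of variance all stay at or below 5.8% in every structure tried. With a strict rule applied to the 15 changes, the procedure may have performed acceptably. All of this stands.

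The six-region count is also only a possibility. The SAP mentions multiple regions as the reason for correcting, not as the PCA input, and its wording fits a PCA over the 15 comparisons at least as well. The 11.8% is therefore conditional. Resistance to volume conduction within a pair does not show that changes across pairs are uncorrelated.

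A reader might also infer that the threshold could be steered through the choice of PCA input. The documents do not show this. The protocol has the data coded and the analyst blinded to session type, which limits that risk without removing it.

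The defence does not rescue the Bonferroni sentence, and it does not turn the PCA count into a guarantee. Nor is naming the rule enough: a fully specified count below 15 still lacks a bound at the nominal level, while a method that has one and also uses the observed correlation is available.

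**Conclusion.** The concern holds in limited form. The reason given for rejecting Bonferroni is wrong, and the method adopted does not guarantee family-wise error control over the 15 pairs. At an assumed two-sided 5% level, the simulated error is about 2% to 26% depending on the rule and correlation, and 11.8% for independent tests if the count were six.

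A reader might go further and conclude that the trial's threshold fails to hold 5%. The documents do not support that. With no alpha, target error rate, PCA input, rule or count stated, the actual rate cannot be computed, and it may be near or below 5%. The level, the error rate to be controlled and all correlation structures used here are assumptions.

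**What to change.** 1. Correct the Bonferroni sentence: the method is valid under any dependence and can be conservative under positive correlation.
2. State alpha, and define the family as the 15 active-versus-sham pairs within each EEG data type.
3. For those 15 changes, replace the PCA threshold with a sign-flip permutation of the maximum signed-rank statistic. Flip each child's whole 15-pair vector of active-minus-sham changes together, so that the observed correlation is kept. Randomised session order supports the flip under the null of no difference between active and sham, which includes no carry-over. This meets the SAP's worry about over-conservatism directly.
4. Report Holm-adjusted p-values beside it. Holm is valid under any dependence and never less powerful than Bonferroni.
5. Label the 30 within-session tests (15 pairs x 2 sessions) descriptive, or give them their own adjustment.
6. The protocol's single named pair may be tested on its own first, without the 15-fold correction. Say whether it gates the remaining pairs. If it does not, the named pair and the 15-pair family are separate claims at 5% each, with a joint bound of 5% + 5% = 10%.

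Cost: the SAP is written in the past tense, so this is a revision of the text plus a re-run of adjusted p-values on existing data, to be reported as such. The new threshold may be stricter than the one used, and some pairs may lose significance.
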